### 2.3.3 Inclusion criteria

The inclusion criteria for the case group in this study comprise neonates (aged 0–28 days or a maximum post-menstrual age of 42 weeks) with a gestational age of 28–36 weeks who are admitted to the neonatal high care unit (NHCU) and neonatal intensive care unit (NICU) of [name] General Hospital, Bandung, and Bandung Kiwari Regional Hospital, and meet the following criteria:

- Patients diagnosed with neonatal sepsis confirmed by blood or cerebrospinal fluid (CSF) culture, OR patients meeting the criteria for suspected sepsis based on a modified Tollner sepsis score of  $\geq 5$ , OR Sepsis Prediction Score  $\geq 3$ .
- Parents or legal guardians are willing to participate in the study and have signed the informed consent form.

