## 2.4. Design and Intervention

This study is an analytical experimental study with a randomized controlled trial (RCT) design. All samples that meet the inclusion and exclusion criteria will be enrolled as study subjects. Subject characteristics data will be obtained from the patient's medical records. This was an open-label trial due to the nature of the nutritional intervention (NPO vs. enteral).

Subjects were subsequently allocated into three groups:

- Group 1: Subjects requiring medical fasting (NPO) due to their clinical condition, who received antibiotics alone.
- Group 2: Subjects able to tolerate enteral nutrition, who received antibiotics plus Vitamin D3 supplementation of 400 IU once daily for 7 days.
- Group 3: Subjects able to tolerate enteral nutrition, who received antibiotics plus Vitamin D3 supplementation of 800 IU once daily for 7 days.

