## 2.5. Randomisation and Blinding

### 2.5.1 Randomisation Procedures

Randomization was performed using a computer-generated random number sequence and allocated by the author.

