## 2.6. Sample Size

Samples will be drawn from study subjects who meet the inclusion criteria. The determination of the sample size is tailored to the study objectives and the type of data involved. This study utilizes a specific design, namely unpaired (non-paired) categorical-numeric analytical design. Therefore, the determination of the sample size is based on statistical calculation, setting a 95% confidence level and an 80% power of test (power). Thus, the minimum sample size for each group is 19 subjects. Therefore, the total minimum sample size for the three groups is 57 patients.

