## 4 DESCRIPTIVE STATISTICS

### 4.1. Recruitment and Follow-up

#### 4.2. Baseline Characteristics

Baseline population will be summarised using mean and standard deviations or median and interquartile range.

Variable	Control (n=...)	Vitamin D 400 IU (n=...)	Vitamin D 800 IU (n=...)	p value
Gender, n (%)				
Male				
Female				
Age (days), Mean/Median (SD/IQR)				
Gestational age (weeks), Mean/Median (SD/IQR)				
Gestational age, n (%)				
32–<37 weeks				
28–<32 weeks				
Birth weight (gram), Mean/Median (SD/IQR)				
Birth weight, n (%)				
<1000 gram				
1000–<1500 gram				
1500–<2500 gram				
≥2500 gram				
Respiratory support, n (%)				
Low Flow				
CPAP/NIV				
Ventilator				
Vitamin D (ng/mL), Mean/Median (SD/IQR)				
Classification of vitamin D status				
Sufficient				
Insufficient				
Deficient				

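### The randomised 400 v 800 IU comparison should be adjusted for one maturity covariate and the Day-0 value; the plan uses birth weight and gestational age only descriptively

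*Combined protocol and SAP*

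**What the plan says.** - **Doses.** Section 2.4 gives Group 2 "antibiotics plus Vitamin D3 supplementation of 400 IU once daily for 7 days" and Group 3 "antibiotics plus Vitamin D3 supplementation of 800 IU once daily for 7 days". Neither dose has a weight term.
- **Who is dosed.** Section 2.3.3 admits neonates "with a gestational age of 28–36 weeks" and sets no weight limit. The empty baseline table in Section 4.2 has birth-weight rows running from below 1000 g to 2500 g and above, and gestational-age rows split at 32 weeks.
- **Allocation.** The whole of Section 2.5.1 reads "Randomization was performed using a computer-generated random number sequence and allocated by the author". It mentions no strata, blocks or minimisation. Under the synopsis, only the infants who can be fed enterally are randomised, that is, Groups 2 and 3.
- **Use of the covariates.** Section 4.2 states "Baseline population will be summarised using mean and standard deviations or median and interquartile range", and its table has a p-value column. Birth weight and gestational age appear in no other planned analysis.
- **Outcome analysis.** Section 3 names no model and no covariate. The nearest indication is in Section 2.6, which identifies the design behind the sample size: "namely unpaired (non-paired) categorical-numeric analytical design".

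**The concern.** The trial will hold, for every infant, two baseline measures of maturity that may well be related to the sepsis scores and CRP. As written, neither enters an outcome analysis. With 19 infants in each randomised arm, one arm can by chance receive the less mature infants. An unadjusted comparison then attributes part of the resulting outcome difference to the dose. Even without a visible imbalance, leaving out a prognostic covariate keeps its variation in the error term.

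The p-value column in the baseline table may look like a safeguard, but at this size an imbalance large enough to matter can easily be non-significant.

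**Working it through.** **Inputs.** From the documents: 19 per group and 57 in total, 95% confidence and 80% power (Section 2.6); doses of 400 and 800 IU (Section 2.4); birth-weight limits of 1000 g and 2500 g (table in Section 4.2). Assumed, because the documents do not give it: the correlation ρ between the covariate and the outcome, taken as 0.3 to 0.5.

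**1. The plan's own figure.** 3 × 19 = 57 agrees with the stated total. The 19 cannot be derived, because no effect size or SD is given. Solving the two-sided normal formula n = 2(1.96 + 0.842)²/d² backwards, d = 0.909 gives 15.70/0.826 = 19.0. Any d from 0.909 to 0.933 rounds up to 19.

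**2. Chance imbalance between the randomised arms.** The standard error of a standardised baseline difference is √(2/19) = 0.324.
- Over 0.3 SD: 0.3/0.324 = 0.92, probability about 36%.
- Over 0.5 SD: 0.5/0.324 = 1.54, probability about 12%.
- Over 0.65 SD: 0.65/0.324 = 2.00, probability about 4.5%.

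The 5% significance limit lies at 1.96 × 0.324 = 0.64 SD. A difference of 0.5 SD therefore has p of about 0.12 and would pass as balanced.

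**3. Consequence when the imbalance is 0.5 SD.** The unadjusted difference shifts by ρ × 0.5 outcome SD:
- ρ = 0.3: shift 0.15 SD, conditional type I error about 6.4%.
- ρ = 0.5: shift 0.25 SD, conditional type I error about 8.6%.

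The conditional error is the probability that a normal variable with mean ρ × 0.5/0.324 and SD √(1 − ρ²) falls outside ±1.96.

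**4. Gain from adjustment.** Residual variance is multiplied by 1 − ρ². With d = 0.909 and 19 per arm, power = Φ(d√(19/2)/√(1 − ρ²) − 1.96):
- Unadjusted: 0.909 × 3.082 = 2.80, power 80%.
- ρ = 0.3: 2.80/0.954 = 2.94, power about 84%.
- ρ = 0.5: 2.80/0.866 = 3.24, power about 90%.

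With two covariates, ρ is their multiple correlation with the outcome.

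**5. Dose per kg.** At 1000 g the doses are 400 and 800 IU/kg; at 2500 g they are 160 and 320 IU/kg. That is a 2.5-fold range within an arm if such infants enrol. If only infants of 1500–2500 g enrol, the range is 2.5/1.5 = 1.67-fold. Simulation with assumed weights (mean 1.5–1.7 kg, SD 0.4–0.5 kg) centres the 800:400 ratio of arm-mean IU/kg on 2.0. The widest 95% range was 1.62 to 2.46, and the order of the arms never reversed.

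**The case against.** Randomisation already makes the unadjusted comparison unbiased on average, and its 5% error rate allows for chance imbalance. The 12% applies to any continuous covariate in any trial of 19 v 19. The precision gain rests on a correlation that the documents do not give. All of this stands: the case for adjustment is better precision and removal of conditional bias, not rescue of an invalid comparison.

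It can also be said that Section 2.6 describes a sample-size formula and that the SAP has no outcome model from which covariates could have been omitted. That is accurate. The covariates are used only descriptively because no outcome analysis has been specified, and writing one is the occasion to include them.

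Three stronger readings are tempting and are not supported:
- *Each arm will span at least 2.5-fold in IU/kg.* The limits come from an empty table with no weight distribution behind it. They are birth weights, while infants may enter at up to 28 days of age or 42 weeks' post-menstrual age.
- *Variation in IU/kg confounds the dose comparison.* The randomised treatments are flat 400 and 800 IU. Variation per kg is heterogeneity of exposure within each arm. Individual infants can overlap (400 IU at 1000 g is 400 IU/kg; 800 IU at 2500 g is 320 IU/kg), but the contrast between arms stays near 2:1 under the assumed weights.
- *Allocation is simple and unstratified.* Section 2.5.1 is silent; it does not say so.

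Finally, the stated objectives compare vitamin D with antibiotics alone, that is, with Group 1, which is formed by fasting status. That imbalance is systematic and is the larger problem. The present point does not touch it.

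**Conclusion.** The point holds as an inexpensive improvement to the randomised 400 v 800 IU comparison, and no further. The plan collects maturity covariates and uses them only for description. With 19 per arm there is about a 12% chance of an imbalance above 0.5 SD in any one of them. At an imbalance of 0.5 SD, the shift is 0.15–0.25 outcome SD and the conditional type I error about 6.4–8.6%, for assumed correlations of 0.3–0.5. Over the same range, adjustment would raise power from 80% to about 84–90%, if 19 per arm does give 80% unadjusted. With a correlation near zero there would be almost no gain.

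A reader might infer that the flat doses make the comparison of the two arms invalid. The documents do not support that.

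**What to change.** In the SAP, analyse each outcome (modified Tollner score, Sepsis Prediction Score, CRP) for 400 v 800 IU by ANCOVA. Include two prespecified covariates: the Day-0 value of that outcome, which Section 3.3 already defines as baseline, and one continuous maturity measure. The latter should be gestational age or birth weight, chosen before outcome data are seen. Do not use both, since they are likely to be collinear and the sample is small. Keep the baseline table, but drop its p values as a check of balance.

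State in Section 2.5.1 whether allocation was stratified and, if it was, include the stratum in the model. Introducing permuted blocks within strata is not required for this fix. In an open-label trial where the author allocates, small blocks would make the next assignment easier to guess. Section 2.5.1 is in the past tense, so the list may already exist; the adjustment is available either way.

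A table of IU/kg/day by arm is optional and descriptive. It would need a Day-0 weight, which the baseline table does not list.

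The cost is SAP wording and one or two degrees of freedom: 38 infants in two arms leave 36, and two covariates leave 34. No extra patients are needed and no dose changes. The comparison with Group 1 needs its own remedy.

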## 2.5. Randomisation and Blinding

### 2.5.1 Randomisation Procedures

Randomization was performed using a computer-generated random number sequence and allocated by the author.

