## 2. STUDY SYNOPSIS

This will be a randomized, multi-centered clinical trial. Participants will include preterm neonates diagnosed with neonatal sepsis who are treated with antibiotics. All eligible patients with parental consent, who cannot tolerate enteral feed will be assigned as Group 1 (antibiotic only). All eligible patients with parental consent, who can tolerate enteral feed enrolled into the trial will be randomized into two treatment groups. Group 2 will receive vitamin D as adjuvant therapy (400 IU) for seven days. Group 3 will receive vitamin D as adjuvant therapy (800 IU) for seven days. Each patient will undergo clinical assessments and blood examination at the beginning and end of each treatment period.

Study assessments will include the sepsis score (Tollner score and sepsis prediction score) and C-reactive protein examination.

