## 2.3. Study Population

### 2.3.1 Number of Participants

We aim to recruit minimum of fifty-seven neonates (19 neonates of each group) aged between 0 and 28 days old or maximum post menstrual age 42 weeks with sepsis.

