### Study Protocol:

1. **Sampling Stage:** Sampling will be conducted in the NHCU and NICU wards of [name] General Hospital Bandung and Bandung Kiwari Regional Hospital Bandung.
2. **Informed Consent:** A verbal and written explanation of the entire study (informed consent) will be provided to the parents/guardians of the study subjects.
3. **Enrolment:** The parents/guardians of the study subjects who agree to the study procedures will then sign the consent form.
4. **Screening:** The researcher will conduct interviews to obtain general data, maternal history, and birth history to identify subjects who meet the inclusion and exclusion criteria.
5. **Blood Sample Collection:** Peripheral venous blood samples will be collected from the case and control subjects twice (on Day 0 and Day 7). Each collection will be approximately for the examination of Vitamin D levels (i.e., 25(OH)D), hematology, peripheral blood smear morphology, and CRP.
6. **Intervention:** The subject groups who can tolerate enteral feeding will receive Vitamin D3 supplementation of either 400 IU or 800 IU once daily for 7 days.
7. **Sample Processing:** Blood samples will be sent to the Clinical Pathology Laboratory at [name] General Hospital Bandung for sample preparation. The 25(OH)D level examination will utilize a stored biological material (SBM), which will be stored at a temperature of -80°C.

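### No ratio, blocking or stratification by hospital is stated for the 400 v 800 IU list, and no analysis or baseline row would show or adjust for a chance hospital imbalance

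*Combined protocol and SAP*

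**What the plan says.** The whole of section 2.5.1 is one sentence: "Randomization was performed using a computer-generated random number sequence and allocated by the author". No section gives an allocation ratio, a block scheme, a stratification factor or a list for each site.

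The synopsis limits randomisation to fed infants: "All eligible patients with parental consent, who can tolerate enteral feed enrolled into the trial will be randomized into two treatment groups". The antibiotic-only group is formed by clinical condition, namely those "who cannot tolerate enteral feed will be assigned as Group 1 (antibiotic only").

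Two hospitals recruit, each from high-care and intensive-care wards (2.3.3, and step 1 of the study protocol list in 2.7: "Sampling will be conducted in the NHCU and NICU wards of [name] General Hospital Bandung and Bandung Kiwari Regional Hospital Bandung"). How many infants each will contribute is not given.

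On numbers, 2.3.1 says "We aim to recruit minimum of fifty-seven neonates (19 neonates of each group") and 2.6 says "Thus, the minimum sample size for each group is 19 subjects". Both are minimums.

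The baseline table in 4.2 covers sex, age, gestational age, birth weight, respiratory support and vitamin D status. It has no row for hospital. Section 3 describes no model that includes hospital.

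**The concern.** The 400 v 800 IU contrast is the only one in the trial that randomisation can protect, and at the stated minimum it rests on 38 infants. Without stratification, a list of that length can by chance put noticeably more of one hospital's infants in one dose arm. If the hospitals then differ in background care or in how the sepsis scores are recorded, the estimated dose difference carries part of that hospital difference. Even where the arms are balanced, between-hospital variation stays in the error term if hospital is not in the model.

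The outcomes concerned are both sepsis scores and CRP. With no hospital row in the baseline table, a reader of the results could not tell whether an imbalance had occurred.

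**Working it through.** **Inputs.** From the documents: at least 19 per group (2.3.1, 2.6); two randomised groups (synopsis); two hospitals (2.3.3, 2.7); 95% confidence and 80% power (2.6). Assumed: simple 1:1 randomisation stopping at 38 infants; 4 to 19 of the 38 at the smaller hospital; two-sided 5% test; normal approximation.

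**The plan's own figure.** 3 × 19 = 57 agrees with 2.6. The 19 itself cannot be reproduced, because no effect size, SD or sidedness is given. Solving backwards, d = √(2/n) × (1.960 + 0.842): n = 19 gives 0.909 and n = 18 gives 0.934. So 19 per group corresponds to a difference of about 0.91 to 0.93 SD (two-sided). The randomised contrast has 2 × 19 = 38 infants.

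**Hospital balance.** Let m infants come from the smaller hospital and 38 − m from the other. Let i ~ Binomial(m, 0.5) and j ~ Binomial(38 − m, 0.5) be the numbers given 400 IU, and a = i + j. The difference in hospital share between the arms is |i/a − (m − i)/(38 − a)|. Summing exactly over all i and j:

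| Smaller hospital, m of 38 | P(difference ≥ 20 points) | P(difference ≥ 30 points) |
|---|---|---|
| 4 | 5.6% | 0.1% |
| 8 | 15.1% | 2.4% |
| 12 | 20.5% | 5.4% |
| 16 | 21.8% | 6.9% |
| 19 | 25.6% | 7.4% |

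**What an imbalance would do.** The shift in the dose contrast is the share difference × the hospital effect. The documents give no hospital effect. With an assumed 0.5 SD, a 20-point imbalance shifts the contrast by 0.20 × 0.5 = 0.10 SD, against the 0.91 to 0.93 SD implied by 19 per group.

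**Arm sizes.** Under Binomial(38, 0.5), P(19/19) = 12.9%, so one arm falls below 19 with probability 87.1%. P(22/16 or more uneven) = 41.8%. Power is Φ(d√(n₁n₂/(n₁+n₂)) − 1.960) with d = 0.909:

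- 19/19: 80.0%
- 16/22: 0.909 × √(352/38) − 1.960 = 0.806, so 79.0%
- 14/24: 77.1%
- average over all splits: 78.9%

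If recruitment instead continues until both arms reach 19, the mean number randomised is about 43.

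**Effect of the remedy.** In 8,000 simulated trials for each value of m, with permuted blocks of 4 listed separately by hospital, the smaller arm was never below 18 and the share difference never exceeded about 5 points. With blocks of up to 6, the arms can differ by at most 3 infants within a hospital. The worst case is +3 at one hospital and −3 at the other, which gives 19/19 and a share difference of 3/19 = 15.8 points, still below 20.

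**The case against.** The strongest reply is that simple randomisation is valid. Chance imbalance is already allowed for in the error rate of the test, so it is not bias. That stands: the loss is in precision and in how readily one small realised trial can be interpreted.

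A reader might infer four stronger things, none of which the documents support.

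- *That the list is unrestricted.* Section 2.5.1 is silent. A computer-generated sequence could have been blocked or made site by site. The percentages above hold only if it was not.
- *That care differs between the hospitals.* No section describes antibiotic or intensive-care practice at either hospital, so the size of any harm is unknown.
- *That missing 19 per arm is a serious loss.* Nineteen is a minimum, so recruitment may go past 38. If it stops there, the average cost is 80.0 − 78.9 = 1.1 power points.
- *That the imbalance risk is as high as 30%.* Fixing exactly 19 per arm (hypergeometric) with a 12/26 hospital split gives 29.5% at a 20-point cut-off. But it falls to 7.9% at 22 points, because 4/19 = 21.1 points is one of the few possible values. That model also fixes an arm split that simple randomisation produces only 12.9% of the time.

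It is also fair to object that the objectives in 2.1 and 2.2 compare each dose with antibiotics alone. That group is not randomised, so nothing done to the 400 v 800 IU list protects those comparisons. Finally, blocking adds predictability in an open-label trial in which the author allocates. This is a reason to avoid very small blocks, but it does not remove the case for stratifying.

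**Conclusion.** The point holds as a modest, low-cost design improvement. The plan states no ratio, blocking or stratification by hospital, and nothing in the baseline table or the described analyses would show or adjust for a hospital imbalance in the only randomised contrast. If the list is simple 1:1 randomisation of 38 infants, an imbalance of 20 points or more has about a 15% to 26% chance with 8 to 19 infants at the smaller hospital, and 5.6% with 4. These figures depend on the assumed hospital splits, on stopping at 38 and on the chosen cut-off. The consequence is added variance, and chance confounding if the hospitals differ. Unequal arm sizes are a minor part of the point.

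**What to change.** - **2.5.1:** state a 1:1 ratio, and generate a separate 400 v 800 IU list for each hospital in randomly varying permuted blocks whose sizes are not disclosed to those who enrol (for example 4 and 6; not 2, which is too easily guessed here).
- **Section 3:** include hospital as a fixed factor in the 400 v 800 IU models for both sepsis scores and CRP.
- **4.2:** add a row for hospital to the baseline table.
- **If allocation has already taken place** (2.5.1 is written in the past tense): report the method actually used, and add the hospital term and the baseline row.

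**Cost.** A new list, one model term and one table row. The term uses one degree of freedom: with 38 infants and dose as the only other term, the residual falls from 38 − 2 = 36 to 38 − 3 = 35. Blocks leave some predictability in an open-label trial, which varying and undisclosed sizes limit but do not remove. The change does nothing for comparisons with Group 1.

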## 2.6. Sample Size

Samples will be drawn from study subjects who meet the inclusion criteria. The determination of the sample size is tailored to the study objectives and the type of data involved. This study utilizes a specific design, namely unpaired (non-paired) categorical-numeric analytical design. Therefore, the determination of the sample size is based on statistical calculation, setting a 95% confidence level and an 80% power of test (power). Thus, the minimum sample size for each group is 19 subjects. Therefore, the total minimum sample size for the three groups is 57 patients.

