### 2.3.2 Eligibility Criteria

Participants will be assigned to a randomised study treatment only if they meet all inclusion criteria and none of the exclusion criteria.

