### 2.3.4 Exclusion criteria

Participants meeting any of the following criteria will be excluded from the study:

- Patients with major congenital malformations, including anencephaly, encephalocele, holoprosencephaly, hydrocephalus, meningomyelocele, spina bifida, omphalocele, gastroschisis, or congenital heart disease.
- Patients who were initially able to tolerate enteral feeding but developed a medical condition requiring fasting (NPO/Nil Per Os) during the 7-day monitoring period.
- Patients who initially required fasting (due to a medical condition) but became able to tolerate enteral feeding during the 7-day monitoring period.

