#### **3.4. Definition of analysis populations**

Data from this study will be analysed as a per-protocol analysis. Data from all participants who are randomised will be included in the per-protocol analysis.

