#### **3.8. Handling of Missing Data**

It is inevitable that some data will be missing. If less than ten percent of the total data is missing then no change to the analysis will be made.

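### If 19 per group means infants analysed, the 80% power is not secured: recruitment has the same minimum with no stated loss allowance, removals after assignment conflict with the analysis set, and the Day-0 scores go unused

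*Combined protocol and SAP*

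**What the plan says.** **Sample size.** Section 2.6 sizes the trial by "setting a 95% confidence level and an 80% power of test (power). Thus, the minimum sample size for each group is 19 subjects", hence 57 in total. Section 2.3.1 uses the same figure for recruitment: "We aim to recruit minimum of fifty-seven neonates (19 neonates of each group"). Neither section mentions loss, replacement or a higher target.

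**Removals.** Section 2.3.2 makes the criteria a condition of entry: "Participants will be assigned to a randomised study treatment only if they meet all inclusion criteria and none of the exclusion criteria". Yet two of the three exclusions in Section 2.3.4 are later events. One removes initially fed infants who "developed a medical condition requiring fasting (NPO/Nil Per Os) during the 7-day monitoring period". The other removes initially fasting infants who "became able to tolerate enteral feeding during the 7-day monitoring period".

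**Analysis set and missing data.** Section 3.4 labels the analysis per-protocol and adds: "Data from all participants who are randomised will be included in the per-protocol analysis". Section 3.8 begins "It is inevitable that some data will be missing" and continues: "If less than ten percent of the total data is missing then no change to the analysis will be made".

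**Groups and Day-0 scores.** By the synopsis and Section 2.4, Group 1 is formed by inability to feed enterally. Only Groups 2 and 3 (400 and 800 IU) are randomised. The synopsis has both sepsis scores assessed at the start and end of treatment, and Section 3.3 defines Day 0 as baseline. No section says how the Day-0 scores enter an analysis, and the baseline table in Section 4.2 does not list them.

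**The concern.** A number that just delivers 80% power has no slack. If it is also the number recruited, each infant removed or missing lowers the power, and the plan foresees both kinds of loss. A report could then quote 80% for a trial that had less, and a non-significant result could be read as absence of effect.

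The second issue is validity. Removing randomised infants because of something that happens after assignment means that the groups compared are no longer the groups randomised. An infant who has to stop feeds may well be one who is doing badly, and the trial is open-label. Whether such infants enter the result should be settled before data are seen. At present one section removes them and another includes them.

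The third is a missed opportunity. The Day-0 scores are already collected and could recover precision in the randomised comparison without another infant.

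**Working it through.** **1. The plan's own figure.** The total reproduces: 3 × 19 = 57. The 19 does not, because the plan gives no difference, SD, test, sidedness or contrast. What it gives is a 5% error rate (from the 95% confidence level), 80% power and an unpaired numeric comparison. The difference for which 19 is the minimum can be back-solved.
- Normal approximation, two-sided: d = √[2(1.960 + 0.842)²/n], which is 0.909 SD at n = 19 and 0.934 SD at n = 18. So 19 is the minimum for 0.91-0.93 SD.
- Two-sided t-test (noncentral t): 0.934 SD at n = 19 and 0.961 SD at n = 18, so 0.93-0.96 SD.
- One-sided t-test: 0.822 and 0.846 SD.

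**2. Power if fewer are analysed.** For the two-sided t-test, power comes from the noncentral t with 2n − 2 degrees of freedom and noncentrality d√(n/2). At 0.934 SD the noncentrality is 2.88, 2.72 and 2.56 for n = 19, 17 and 15.

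| Analysed per group | Power at 0.934 SD | Power at 0.961 SD |
|---|---|---|
| 19 | 80.0% | 82.2% |
| 17 | 75.2% | 77.6% |
| 15 | 69.5% | 72.0% |

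The numbers 17 and 15 are assumed losses of 2/19 = 10.5% and 4/19 = 21.1%. The fall hardly depends on the unstated test. Starting from 80% at 19, the normal approximation gives 75.5% and 70.2%, and the one-sided t-test 75.9% and 71.0%.

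**3. The Section 3.8 threshold.** Suppose its total data are counted as infants, which is an assumption. Ten percent of 57 is 5.7, so 5 infants (8.8%) could be missing with no change to the analysis. Two-group power then averages 75.9% at 0.934 SD and 78.3% at 0.961 SD if the losses are spread at random over the three groups. For the randomised pair alone, 10% of 38 is 3.8, so 3 infants. The splits 19/16 and 18/17 give 76.2% and 76.5% at 0.934 SD, and 78.5% and 78.8% at 0.961 SD.

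**4. The sections side by side.**

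| Section | What it implies for an infant whose feeding status changes on, say, day 4 |
|---|---|
| 2.3.2 | Exclusions are checked before assignment, so this one cannot be applied |
| 2.3.4 | Excluded from the study |
| 3.4, Groups 2 and 3 | Analysed, because randomised |
| 3.4, Group 1 | No rule, because not randomised |

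The number analysed per group is therefore undefined, and with it the loss to set against 19.

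**5. Using the Day-0 score (400 vs 800 IU).** ANCOVA multiplies the error variance by 1 − ρ², where ρ is the Day-0/Day-7 correlation, and uses 2n − 3 degrees of freedom. Chance imbalance at Day 0 multiplies the variance of the difference by 1 + F/(2n − 2), with F on 1 and 2n − 2 degrees of freedom. Averaging over that imbalance, at 19 per group and 0.934 SD:

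| Assumed ρ | Power |
|---|---|
| no covariate | 80.0% |
| 0 | 78.8% |
| 0.3 | 82.4% |
| 0.5 | 89.0% |
| 0.7 | 97.1% |

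The break-even is ρ of about 0.17. With 15 analysed per group, ρ = 0.5 gives 79.8% instead of 69.5%, and ρ = 0.3 gives about 72%. The documents give no value of ρ.

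**The case against.** Section 2.6 speaks of a minimum sample size and never says that 19 infants must be evaluable. Both sections call the figure a minimum, so recruitment may go further. Section 2.4 enrols those who satisfy the inclusion and exclusion criteria, so infants removed under Section 2.3.4 might not count toward the 57. An allowance could even be built in already: 17/0.9 = 18.9 and 15/0.8 = 18.75 both round up to 19. The Section 3.8 rule concerns when to change the analysis and does not forecast loss. All of this stands. A reader might infer that the trial is underpowered, or that 19 must mean evaluable infants; the documents support neither.

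On ANCOVA, the stated objectives (Sections 2.1 and 2.2) compare vitamin D with antibiotics alone and do not name 400 vs 800 IU, so the gain shown applies to a contrast that is not a stated objective. Entry on score thresholds (Section 2.3.3) may narrow the Day-0 spread and lower the correlation. Both points stand. They limit the benefit, but 400 vs 800 IU is the only randomised comparison in the trial and the possible loss is small.

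None of this answers the conflict between Sections 2.3.2, 2.3.4 and 3.4. Even if removed infants were replaced and the numbers held, leaving out randomised infants because of a later event would still alter the randomised comparison.

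**Conclusion.** The point holds in conditional form. If 19 is the number needed in the analysis, the plan does not secure 80% power, because it recruits to the same minimum and states no allowance for losses that it foresees. The size is about 75-78% with 17 and 69-72% with 15 analysed per group. This rests on a two-sided 5% t-test, a back-solved difference of 0.93-0.96 SD and assumed losses.

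Two parts do not depend on those assumptions. Section 2.3.4 contradicts Sections 2.3.2 and 3.4 for randomised infants, and Section 3.4 leaves Group 1 without an analysis rule. No stated analysis uses the Day-0 scores.

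A reader might also infer that adjusting for Day 0 would make the comparisons with Group 1 fair. It would not: that group is defined by clinical condition, and ANCOVA does not remove the confounding.

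**What to change.** 1. **Reconcile Section 2.3.4 with Sections 2.3.2 and 3.4.** State whether randomised infants whose feeding status changes are analysed, and which Group 1 infants are analysed. The cost is wording, plus obtaining a Day-7 score for any such infant who is to be analysed.

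2. **Add to Section 3:** 'For the randomised 400 vs 800 IU comparison, each Day-7 score will be analysed by ANCOVA with the Day-0 value of the same score as covariate.' Report comparisons with Group 1 as non-randomised. This is a standard model in the planned software and needs no extra infants. It costs about 1.2 points of power if the Day-0/Day-7 correlation is zero and gains above about 0.17.

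3. **In Sections 2.6 and 2.3.1, state whether 19 means recruited or evaluable.** If evaluable, give the power at smaller numbers for the difference and test actually used; the 17 and 15 rows of the power table above show the range to expect under a two-sided t-test. The cost is a less favourable power statement. Recruiting above 57 to cover losses is a separate trade-off for the sponsor and is not needed for this change.
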